## Prognostic evaluation of red blood cell distribution width (RDW) in severe and critical COVID-19 patients monitored in the intensive care unit

### 1. Methodology:

Retrospective, single-center, observational study.

This retrospective study included data from severe and critical COVID-19 patients admitted to the COVID-19 Intensive Care Unit of Ankara University Ibn-i Sina Research and Practice Hospital, Department of Anesthesiology and Reanimation, between June 2020 and May 2024.

---

### 2. Objective of the Study:

COVID-19 has caused significant morbidity and mortality worldwide, particularly among critically ill patients. Early identification of patients at high risk for poor outcomes is crucial. Red cell distribution width (RDW), a measure of the variation in red blood cell size, has emerged as a potential marker of inflammation and has been associated with adverse outcomes in various medical conditions, including COVID-19.

This study aims to investigate the relationship between RDW and mortality in severe and critical patients admitted to our COVID-19 intensive care unit.

- **Primary Objective:** To determine whether RDW can serve as a prognostic marker for mortality in severe and critical COVID-19 patients admitted to the ICU.
- **Secondary Objective:** To evaluate the association of RDW with adverse outcomes such as invasive mechanical ventilation, duration of intubation, and secondary organ damage in severe and critical COVID-19 patients admitted to the ICU.

---

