### 3. Inclusion Criteria:

- Patients over 18 years of age
- Severe and critical COVID-19 patients (with positive PCR test or diagnosed clinically and radiologically)
- Patients followed in the ICU for at least three days
- Patients without hematological malignancy

COVID-19 severity was classified according to the **Diagnosis and Treatment Protocol for Novel Coronavirus Pneumonia (Trial Version 7)** published by the National Health Commission of the People's Republic of China:

- **Severe cases:** Meeting any of the following criteria:
  - Respiratory rate (RR)  $\geq$  30 breaths/min
  - Resting oxygen saturation (finger)  $\leq$  93%
  - Arterial partial pressure of oxygen (PaO2)/fraction of inspired oxygen (FiO2)  $\leq$  300 mmHg

- 50% progression of lung lesions within 24–48 hours on imaging
- **Critical cases:** Meeting any of the following criteria:
  - Respiratory failure requiring mechanical ventilation
  - Shock
  - ICU admission required due to organ failure other than respiratory failure

*Reference: National Health Commission & National Administration of Traditional Chinese Medicine. (2020). Diagnosis and treatment protocol for novel coronavirus pneumonia (Trial Version 7). Chinese Medical Journal, 133(09), 1087-1095.*

---

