#### **4. Exclusion Criteria:**

- Patients under 18 years of age
- Patients with hematological malignancies (since RDW levels may be affected)
- Patients who died within three days of ICU admission

---

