#### **Data to be recorded:**

- **Demographics:** Sex, age, body mass index (BMI), number and type of COVID-19 vaccines
- **Comorbidities**
- **Hospitalization data:** Referring department, length of stay, outcome (mortality/discharge), discharge destination
- **At ICU admission:** APACHE II and SOFA scores, days from symptom onset to hospital admission, type of respiratory support, hematological and biochemical laboratory results
- **During follow-up:** Trends in hematological and biochemical laboratory parameters (increase/decrease/normalization), need for invasive/non-invasive mechanical ventilation, duration of intubation, antiviral therapy, development of secondary infections, development of secondary organ failure, mortality/discharge

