#### **6. Statistical Analysis**

- **Sample Size Calculation**

The main hypothesis of the study was to investigate whether there is a difference in RDW levels between patients who survived and those who did not. Based on the study by Lorente et al. (2021), which reported RDW values of  $13.4 \pm 1.5$  and  $14.5 \pm 2.2$ , an effect size of 0.58 was calculated. At a significance level of 0.05 and a statistical power of 0.80, the required sample size was determined to be 110 patients in total. The sample size calculation was performed using the G\*Power software (version 3.1.9.2).

- **Statistical Methods**

Descriptive statistics will be presented as mean  $\pm$  standard deviation (min–max) for normally distributed quantitative variables, as median (min–max) for non-normally distributed variables, and as percentages for categorical variables. To compare two independent groups, the *Independent Samples t-test* will be used when assumptions are met, while the *Mann-Whitney U test* will be applied otherwise. Relationships between categorical variables will be evaluated using the *Chi-Square test*, *Fisher's exact test*, or multi-way Chi-Square test, as appropriate. For comparisons involving more than two groups, *One-Way ANOVA* or the *Kruskal-Wallis test* will be applied depending on the distribution of data. All statistical analyses will be performed using SPSS software (version 11.5).

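### Duration of intubation has no rule for patients who die while intubated, so comparing raw days could dilute or reverse its association with RDW

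*Combined protocol and SAP*

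**What the plan says.** Section 2 (Objective of the Study) sets the secondary objective "To evaluate the association of RDW with adverse outcomes such as invasive mechanical ventilation, duration of intubation, and secondary organ damage". Under Data to be recorded, the follow-up items include "need for invasive/non-invasive mechanical ventilation, duration of intubation", with no definition of start or end, no time horizon and no rule for death.

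Section 6 (Statistical Analysis) gives generic methods: "To compare two independent groups, the *Independent Samples t-test* will be used when assumptions are met, while the *Mann-Whitney U test* will be applied otherwise". It adds ANOVA or Kruskal-Wallis for more than two groups, and chi-square or Fisher's exact test for categorical variables. None is assigned to intubation duration, and no grouping of RDW is stated. There is no time-to-event method, competing-event method or composite.

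The only rules that touch early death are the exclusion in section 4, "Patients who died within three days of ICU admission", and the minimum stay in section 3, "Patients followed in the ICU for at least three days".

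**The concern.** A short intubation can mean early recovery or early death. A mean or rank test on raw days cannot tell the two apart. Under the study's own primary hypothesis, high RDW goes with more deaths, so the event that cuts duration short depends on the predictor being studied.

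Three misleading results are possible. High RDW could appear to go with shorter intubation when it has no effect on extubation. A real prolongation could be mostly missed. Or a real prolongation could appear with the opposite sign. Deaths on the ventilator are to be expected in this population, because respiratory failure needing mechanical ventilation is one of the criteria for a critical case. The three-day exclusion leaves all later deaths on the ventilator in the data.

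**Working it through.** **The plan's own figure.** Nothing is sized for intubation duration. The only calculation, a total of 110, serves the comparison of RDW between survivors and non-survivors. With d = 1.1/√((1.5² + 2.2²)/2) = 0.584, two-sided 5% and 80% power, 110 is reproduced by a Mann-Whitney calculation at the minimum asymptotic relative efficiency of 0.864. It has no bearing on this point.

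**Step 1: closed form.** Let e and m be constant daily hazards of extubation and of death while intubated. Then:

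- mean raw duration = 1/(e + m)
- share dying while intubated = m/(e + m)
- ventilator-free days to day 28, death scored 0 = [e/(e + m)] × [28 − (1 − exp(−28(e + m)))/(e + m)]

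All hazards are assumptions. The three-day exclusion is not applied in this step.

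| Group | e | m | Mean raw days | Die intubated | Ventilator-free days |
|---|---|---|---|---|---|
| Low RDW | 0.060 | 0.040 | 1/0.100 = 10.0 | 40% | 11.2 |
| High RDW, (a) | 0.045 | 0.040 | 1/0.085 = 11.8 | 47% | 9.2 |
| High RDW, (b) | 0.045 | 0.055 | 1/0.100 = 10.0 | 55% | 8.4 |
| High RDW, (c) | 0.045 | 0.080 | 1/0.125 = 8.0 | 64% | 7.3 |
| High RDW, (d) | 0.030 | 0.120 | 1/0.150 = 6.7 | 80% | 4.3 |

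Extubation is slower with high RDW in all four cases. The raw difference is +1.8 days in (a), 0 in (b), −2.0 in (c) and −3.3 in (d). Raw days point the right way only when the death hazard is not raised.

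**Step 2: simulation with the three-day exclusion.** Assumptions: RDW standard normal; exponential times to extubation and to death, mean 20 days each, with hazards multiplied by a hazard ratio (HR) per SD of RDW; intubation starting at ICU admission; duration is the earlier of the two times; deaths before day 3 removed; 70 intubated patients kept; RDW split at the median; Mann-Whitney at two-sided 5%; 4000 runs per scenario.

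*RDW has no effect on extubation (nominal rate of falsely shorter: 2.5%):*

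| Death HR | Median days, high v low RDW | Falsely shorter |
|---|---|---|
| 1.5 | 7.6 v 9.4 | about 13% |
| 2.0 | 7.1 v 10.0 | about 27% |

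Without the exclusion the rates are 19% and 47%, so the exclusion helps but does not cure. Removing every record under three days instead gives 20% and 42%. Milder inputs give 5% (death HR 1.2) and 8% (death HR 1.5, mean time to death 40 days).

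*RDW also slows extubation, death HR 1.5:*

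| Extubation HR | Median days, high v low RDW | Raw days find longer | Cause-specific Cox, continuous RDW |
|---|---|---|---|
| 0.80 | 8.1 v 8.3 | 2% | 24% |
| 0.67 | 8.4 v 7.5 | 9% | 63% |
| 0.50 | 8.9 v 6.2 | 39% | 98% |

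The last column changes two things at once: it handles death and it keeps RDW continuous. At extubation HR 0.67 the like-for-like figure, with the same median split, is 42% against 9%.

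At death HR 2.0 and extubation HR 0.67, the medians are 7.7 v 7.7 days, so the effect is fully masked. At death HR 2.0 and extubation HR 0.80, they reverse to 7.4 v 8.7 days. With no extubation effect, the cause-specific model rejects in about 5% of runs, as it should.

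**The case against.** The strongest reply has four parts.

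- **The criticised analysis is not in the plan.** No section splits RDW or commits to comparing raw days by RDW group. This is true: the plan leaves the handling open. But every test it lists for a quantitative outcome works on means or ranks, so following it leads to raw days in some form.
- **Reversal is overstated.** At death HR 1.5 with a real prolongation, high RDW comes out significantly shorter in about 2.8%, 0.5% and 0% of studies (extubation HR 0.80, 0.67 and 0.50), no more than chance. This stands for that setting, where the usual harm is dilution. Reversal needs a stronger link of RDW with death, as in cases (c) and (d) or at death HR 2.0 with extubation HR 0.80. It is possible, not expected.
- **The inputs are assumed.** The lead case has about 42% of retained patients dying while intubated. With mean extubation time 12 days and mean time to death 40 days (death HR 1.5) the false rate is about 6%; with 40 intubated patients it is about 10%. In the other direction, intubation starting on average 3 days after admission gives about 17% (HR 1.5) and 40% (HR 2.0). The figures are illustrations, not estimates for this study.
- **The stakes are limited and the data may be harder to get.** This is one item under a secondary objective, and the plan records a duration, not event dates. Both are fair. They bear on priority and on the effort needed, not on whether the gap exists.

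**Conclusion.** The concern holds. A named secondary outcome is cut short by the event RDW is hypothesised to predict, and no rule beyond the three-day exclusion deals with it. Under the stated assumptions the false finding of shorter intubation ranges from about 5% to 27% with the exclusion applied and intubation starting at admission, against a nominal 2.5%. A real prolongation at extubation HR 0.67 and death HR 1.5 is detected in 9% of studies by raw days, against 42% by a cause-specific model with the same split.

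The direction of the distortion is not fixed by the design; it depends on how strongly RDW acts on death relative to extubation. If RDW affected extubation only, raw days would not be reversed. The primary mortality result and its sample size are not affected. The plan should be changed, but the point is not critical to the study.

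**What to change.** Specify for this outcome, among intubated patients:

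- **Main analysis:** time from intubation to extubation alive, with death while intubated as a competing event (cause-specific hazard or cumulative incidence) and RDW as a continuous predictor.
- **Beside it:** the hazard of death while intubated, since the two must be read together.
- **Transfers:** censor patients transferred while still intubated, and report their number, because transfer may be informative.
- **Time at risk:** consider starting it at day 3 to match the exclusion. In the simulation with no extubation effect this moved the median HR only from 1.01–1.02 to 1.00.
- **Raw days:** descriptive only, separately for survivors and non-survivors.
- **Optional support:** ventilator-free days to day 28 with deaths scored 0, shown next to the mortality result.

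The cost is SAP wording, one derived variable, and intubation, extubation and death dates from the existing records, whose availability should be confirmed. A cause-specific Cox model is an ordinary Cox model with deaths censored; the sponsor should check that the named SPSS version covers whichever method is chosen.

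Ventilator-free days cannot replace the main analysis because they partly re-express mortality. With no RDW effect on extubation they still rate high RDW significantly worse in 6% (death HR 1.5) to 9% (death HR 2.0) of runs.

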### 3. Inclusion Criteria:

- Patients over 18 years of age
- Severe and critical COVID-19 patients (with positive PCR test or diagnosed clinically and radiologically)
- Patients followed in the ICU for at least three days
- Patients without hematological malignancy

COVID-19 severity was classified according to the **Diagnosis and Treatment Protocol for Novel Coronavirus Pneumonia (Trial Version 7)** published by the National Health Commission of the People's Republic of China:

- **Severe cases:** Meeting any of the following criteria:
  - Respiratory rate (RR)  $\geq$  30 breaths/min
  - Resting oxygen saturation (finger)  $\leq$  93%
  - Arterial partial pressure of oxygen (PaO2)/fraction of inspired oxygen (FiO2)  $\leq$  300 mmHg

- 50% progression of lung lesions within 24–48 hours on imaging
- **Critical cases:** Meeting any of the following criteria:
  - Respiratory failure requiring mechanical ventilation
  - Shock
  - ICU admission required due to organ failure other than respiratory failure

*Reference: National Health Commission & National Administration of Traditional Chinese Medicine. (2020). Diagnosis and treatment protocol for novel coronavirus pneumonia (Trial Version 7). Chinese Medical Journal, 133(09), 1087-1095.*

---

#### **4. Exclusion Criteria:**

- Patients under 18 years of age
- Patients with hematological malignancies (since RDW levels may be affected)
- Patients who died within three days of ICU admission

---

#### **5. Data Collection:**

Patient demographics, clinical features, laboratory results (including RDW), and outcomes will be collected from electronic medical records and patient files.

To ensure patient confidentiality, data will be anonymized. Since all data will be de-identified and analyzed retrospectively, no direct patient contact will be required.

#### **Data to be recorded:**

- **Demographics:** Sex, age, body mass index (BMI), number and type of COVID-19 vaccines
- **Comorbidities**
- **Hospitalization data:** Referring department, length of stay, outcome (mortality/discharge), discharge destination
- **At ICU admission:** APACHE II and SOFA scores, days from symptom onset to hospital admission, type of respiratory support, hematological and biochemical laboratory results
- **During follow-up:** Trends in hematological and biochemical laboratory parameters (increase/decrease/normalization), need for invasive/non-invasive mechanical ventilation, duration of intubation, antiviral therapy, development of secondary infections, development of secondary organ failure, mortality/discharge

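### Illness time is recorded only to hospital admission, RDW is taken at ICU admission, and no adjusted analysis is planned, so independence of an RDW difference from sampling time cannot be shown

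*Combined protocol and SAP*

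**What the plan says.** The primary objective in section 2 is "To determine whether RDW can serve as a prognostic marker for mortality". Section 5 names RDW among the laboratory results to be collected. Its list of data to be recorded puts these items at ICU admission: APACHE II, SOFA, "days from symptom onset to hospital admission", and "type of respiratory support, hematological and biochemical laboratory results".

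The hospitalization items are "Referring department, length of stay, outcome (mortality/discharge), discharge destination". Length of stay appears once, without saying whether it means the hospital or the ICU stay. During follow-up, laboratory values are kept as trend categories. The list contains no ICU admission date, no interval from hospital to ICU admission and no interval from symptom onset to ICU admission.

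Section 6 frames the main hypothesis as a difference in RDW between survivors and non-survivors. It lists t-test or Mann-Whitney, chi-square or Fisher, and ANOVA or Kruskal-Wallis procedures. No regression or other adjusted analysis is listed, and the section does not say which RDW value enters the comparison.

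**The concern.** The illness clock stops at the hospital door, while the blood sample it should describe is drawn at the ICU door. The two coincide for a direct ICU admission. For a ward transfer they differ by the ward stay, and recording a referring department suggests that patients arrive from more than one source.

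Suppose late transfer is associated with death and RDW drifts as the illness goes on. Part of any survivor versus non-survivor difference would then reflect when the sample was drawn. With the opposite pattern, a real association could be masked. This matters for a proposed prognostic marker because illness duration is already known at the bedside. A reader will want to know whether RDW adds to it, and the plan has neither the variable nor the analysis to answer that.

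**Working it through.** **1. What the recorded field measures.** For each patient, onset-to-ICU days = onset-to-hospital days + hospital-to-ICU days. Only the first term on the right is listed. The shortfall is therefore zero for direct admissions and equals the ward stay for transfers.

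**2. Whether other listed fields supply the missing term.** Referring department separates sources of admission but carries no time. Length of stay is a single undefined field. Even if hospital and ICU stays were both captured, their difference would mix ward days before the ICU with ward days after it. Post-ICU days occur mainly in patients who leave the ICU alive, so that proxy would depend on the outcome. Only a coarse split remains.

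**3. Whether the planned analysis would use the term.** Section 6 has no model in which any time variable, including the recorded one, could enter. Adding the field alone would change nothing.

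**4. The plan's own figure.** Inputs from section 6: RDW 13.4 (SD 1.5) and 14.5 (SD 2.2), alpha 0.05, power 0.80, total 110.
- Pooled SD = sqrt((1.5² + 2.2²)/2) = 1.883. Effect size = 1.1/1.883 = 0.584, which agrees with the stated 0.58.
- A two-sided t-test with equal groups needs 94 (d = 0.584) or 96 (d = 0.58). A two-sided Mann-Whitney test at the minimum asymptotic relative efficiency of 0.864 needs 110 (d = 0.584), so 110 can be reproduced. The plan does not state the test or sidedness behind it.
- Nothing in this point changes that number.

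**5. Possible size, on assumed inputs.** The documents give no RDW slope, no pre-ICU stay and no difference in stay by outcome. The assumptions are a slope of 0.02 to 0.10 points per pre-ICU day, a difference in mean pre-ICU days of 1 to 5, and 55 patients per group (section 6 gives only the total).

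Contribution to the RDW difference = slope × difference in days. Standard error = sqrt((1.5² + 2.2²)/55) = 0.359. The last column is the chance that a two-sided t-test is significant from this contribution alone (noncentral t).

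| Slope per day | Difference in days | Contribution | Share of 1.1 | Chance of p < 0.05 |
|---|---|---|---|---|
| 0.02 | 1 | 0.02 | 2% | 5% |
| 0.05 | 3 | 0.15 | 14% | 7% |
| 0.05 | 5 | 0.25 | 23% | 11% |
| 0.10 | 3 | 0.30 | 27% | 13% |
| 0.10 | 5 | 0.50 | 45% | 28% |

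Stretching the assumed difference to 6 days at the steepest slope gives 0.60 points (0.60/1.1 = 55%) and, by the normal approximation, about 39%. The upper end is set entirely by the assumptions.

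**The case against.** The strongest reply is that the plan never claims independence from illness time. It asks whether RDW levels differ by survival. If late transfers die more often and have higher RDW, the levels really do differ, RDW at ICU admission does carry prognostic information, and rejecting the null is correct. This stands. A reader might infer that the percentages above are false-positive rates for the main hypothesis. They are not: they apply only to RDW's value beyond illness time, which is a further question.

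A reader might also infer that the two effects cannot be separated at all, or that the interval is lost. The documents do not support either. Referring department permits a coarse split. The three-day ICU rules in sections 3 and 4 require ICU timing, and the recorded interval requires the hospital admission date, so both ends must already be consulted in the records that are the data source. The gap is an incomplete list of fields.

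It is also fair to say that the missing interval is not the main barrier. APACHE II, SOFA and age are recorded, and no adjustment is planned for them either.

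Finally, recording laboratory trends during follow-up is a general instruction and does not show that RDW drifts before ICU admission. That too stands, and it is why no size is claimed. None of these replies supplies the interval or an analysis that uses it.

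**Conclusion.** The point holds in a limited form. The only illness-time field stops before the baseline sample, and section 6 contains no adjusted analysis. As written, the study therefore cannot show whether an RDW difference between survivors and non-survivors is independent of how late in the illness RDW was sampled.

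The effect may be negligible or material. The illustrative 0.02 to 0.50 points rests wholly on assumed slopes and day differences, and the associated 5% to 28% also on an assumed equal split. Direction is unknown. The conclusion also takes the compared RDW to be the ICU-admission value, which is the natural reading of section 5 but is not stated in section 6. The documents do not support calling an observed difference spurious, or the unadjusted test invalid for its own hypothesis. This is a worthwhile, inexpensive improvement to what the study can conclude.

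**What to change.** In section 5, under the items recorded at ICU admission, add two fields: the number of days from first symptoms to ICU entry, and the number of days between hospital and ICU entry. State that the RDW compared is the ICU-admission value.

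In section 6, keep the unadjusted comparison. Add a prespecified analysis of RDW and mortality, for example logistic regression, adjusted for the symptom-to-ICU interval. Show the results separately for direct admissions and ward transfers as well, using the referring department already listed.

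The cost is one extra date per patient from records already in use, one covariate and one stratified table. Numbers within each stratum will be smaller, so that table should be read as descriptive. Because the data are to be anonymized, the intervals are best computed at extraction. The total of 110 need not change for this point.
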